3.1.4 Wear-Time Field Trial-Secondary

- Null hypothesis: Mean difference $(QuickSIN_{PRO-FIT} - QuickSIN_{SELF-FIT}) \geq 1.5$ dB
- Alternative hypothesis: Mean difference $(QuickSIN_{PRO-FIT} - QuickSIN_{SELF-FIT}) < 1.5$ dB

3.1.5 In-Lab Session-Reliability Component-Primary

- Null hypothesis: Mean $|REAG_{SELF-FIT A} - REAG_{SELF-FIT B}| \geq 2.5$ dB
- Alternative hypothesis: Mean $|REAG_{SELF-FIT A} - REAG_{SELF-FIT B}| < 2.5$ dB

3.1.6 In-Lab Session-Reliability Component-Secondary

- Null hypothesis: Mean difference $|QuickSIN_{SELF-FIT A} - QuickSIN_{SELF-FIT B}| \geq 1.5$ dB
- Alternative hypothesis: Mean difference $|QuickSIN_{SELF-FIT A} - QuickSIN_{SELF-FIT B}| < 1.5$ dB

3.2 Study Endpoints

3.2.1 Primary Effectiveness Endpoint(s)

For the validation component of the immediate in-lab session comparisons, Real-Ear Aided Gain (REAG) will be measured using both an audiology-best-practices (professional) hearing aid fitting (PRO-FIT) and a self-fitting method (SELF-FIT).

- Success criterion is defined as SELF-FIT REAG is equivalent to PRO-FIT NAL-NL2 prescription REAG targets based on the average real-ear aided gain at 500, 1000, 2000 and 4000 Hz.

For the reliability component of the immediate in-lab session comparisons, Real-Ear Aided Gain (REAG) will be measured twice (A, B) using the SELF-FIT method.

- Success criterion is four-frequency average REAG for SELF-FIT B is equivalent to the REAG for SELF-FIT A based on the average real-ear aided gain at 500, 1000, 2000 and 4000 Hz.

For the wear-time crossover field trial, the APHAB will be measured following both an audiology best-practices hearing aid fitting (PRO-FIT) and a self-fitting method (SELF-FIT).

- Success criterion is defined as SELF-FIT APHAB global score is non-inferior to PRO-FIT APHAB global scores following completion of the wear-time field trial.

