1.5.2 Anticipated Adverse Effects

1.5.2.1 *Potential risks related to using Jabra Enhance Plus as a treatment vs. standard of care*

Compared to the standard-of-care fitting, the only anticipated risks involve the improper self-selection of device settings such that either too little or too much gain will be selected. The maximum possible gain, however, has been limited to minimize the risk to hearing from device use.

1.5.2.2 *Potential risks associated with patient population*

Because the app used to fit and control the device requires some familiarity with such apps, the user may experience some frustration when initially learning how to fit and control the device.

1.5.2.3 *Possible interactions and concomitant treatments*

Because both new and experienced hearing aid users are to be included, experienced user may be frustrated with the differences between the Jabra Enhance Plus device and their own hearing aids, including differences in sound quality and adjustment.

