3.0 OBJECTIVES OF RESEARCH STUDY

3.1 Hypotheses

3.1.1 In-lab validation component-Primary

- Null hypothesis: Mean $|REAG_{PRO-FIT} - REAG_{SELF-FIT}| \geq 2.5$ dB
- Alternative hypothesis: Mean $|REAG_{PRO-FIT} - REAG_{SELF-FIT}| < 2.5$ dB

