8.1.2 In-Lab *REAG – Validity* (initial Pro-Fit vs initial Self-Fit A)

- i. Paired-sample t-test for equivalence of the means of the initial-fit settings of the SELF-FIT A procedure to the means of the initial-fit settings of the PRO-FIT procedure
- ii. Supplementary analyses will include examination of the distribution of differences in dB between the four-frequency average REAGs for initial-fit settings of the SELF-FIT A procedure and initial-fit settings of the PRO-FIT procedure, as well as computation of correlation coefficients between the two measures.

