8.4 Pass/Fail Criteria of the Study

For the in-lab session, the primary effectiveness endpoint will be assessed by the differences in acoustical real-ear aided gain (REAG), a gold-standard measure for the acoustical function of hearing devices for the study population. This endpoint will be used to assess mean absolute-value differences between two replications of the self-fit method (reliability) and between the self-fit and professional-fit methods (validity or effectiveness).

For the wear-time trial, the primary outcome measure is a widely used clinical self-report measure of benefit (Abbreviated Profile of Hearing Aid Benefit, APHAB). The APHAB is also a gold-standard, validated assessment of hearing-aid benefit relevant for the study population.

Secondary effectiveness endpoints for both the laboratory and field-trial components will be assessed by a standardized measure of speech communication in noise, the QuickSIN. This is a widely used clinical measure of an adult's ability to understand speech in noise and is closely tied to the wearer's primary complaint, difficulty communicating in noise.

Overall study success will be defined by meeting all primary endpoints for the reliability, effectiveness, and safety of the devices and the self-fitting process in the laboratory and field-trial components of this study. Effectiveness outcomes from the SELF-FIT process should be equivalent to those of the PRO-FIT method in the in-lab session and non-inferior to PRO-FIT in the wear-time trial for the study to be considered successful.

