13.1 Management of Data

High data quality standards will be maintained, and processes and procedures utilized to repeatedly ensure that the data are as clean and accurate as possible when presented for analysis. Data quality will be enhanced through a series of programmed data quality checks that automatically detect out of range or anomalous data.

The following practices are adopted to ensure data integrity and participant safety:

1. Data, including outcomes data, should not be shared with GN Hearing A/S until study completion. There are two components to this study: (1) in-lab session (Visit 1); and wear-time crossover trial (Visits 2 and 3). Outcome data can be shared with GN Hearing A/S at the completion of each component to this study. That is, the results from Visit 1 can be shared with the sponsor as soon as they are available and prior to the completion of the entire study.
2. The site investigators should be blinded from the raw data and the research staff on site should enter the data into an electronic database (REDCap). Weekly reports of completed data for each visit will be generated by research staff at each site and will be sent to [name]. Progress reports, generated by [name], will tabulate the number of subjects who have complete data for Visit 1, Visit 2, and Visit 3, for each site separately and combined. Such progress reports will be provided via email to GN Hearing A/S ([name] and [name]) and shared with the site investigators ([name], [name]) on a weekly basis.
3. [name] will monitor the quality of the data exported from REDCap. PRO-FIT REAG values will be checked to determine that they are reasonable, within 5-7 dB of NAL targets, for the measured pure-tone hearing loss for that participant. The pattern across frequency for the REAG differences between test and retest will also be examined to assess data validity. Such differences should generally be less than 5 dB at a given frequency and also should not decrease with increasing frequency. Concerns about the quality of data being gathered will be shared with each site investigator and GN Hearing A/S as soon as possible.

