16.0 ADDITIONAL STUDY MATERIALS

ATTACHMENT A: See attached clinical study user's manual for Jabra Enhance Plus

ATTACHMENT B: Real-ear measurement details

A. **SELF-FIT A & B:** Personalization begins with an estimate of hearing acuity obtained through the Jabra Enhance Plus. The hearing acuity measurements are used internally by the device and are not shared with the hearing aid wearer. Once this step has been completed, devices will apply NAL-NL2 gain prescriptions directly using the estimated hearing acuity to generate the initial fit. For the clinical validation study, probe-tube microphone measures of the REUR and REAR (REAG=REAR in input) will be obtained on the initial fit for a 65-dB speech input using the Audioscan Verifit real-ear measurement system, with instructions as follows:

[figure not shown]
- i. Use the Audioscan Verifit (see procedure below) to measure Real Ear Aided Response (REAR) using the GN-supplied dome/probe tube assembly.
- ii. Without adjusting the gain, determine how close the 65 dB-Input referenced Response curve from the output of the device is to the NAL-NL2 65 dB REAR Targets in the Verifit 1 or 2.
- iii. Audioscan includes a method for saving measurements to a USB drive. Please use this method for saving the REAR measurements and Targets for analysis of the output.
- iv. The file saved to the USB drive should include a .html or .csv file with frequency-specific values that can be used for plotting and analyzing the results.

B. **PRO-FIT:** Audiometric thresholds will be imported, and the devices programmed using custom device programming software (AlgoLabTest) and configured for NAL-NL2 target gains. Probe-tube microphone measures of the REUR and REAR (REAG=REAR-REUR) will be obtained for a 65-dB speech input using the Audioscan Verifit real-ear measurement system, with instructions as follows:

- i. Use the Audioscan Verifit (see procedure below) to measure Real Ear Aided Response (REAR) using the GN-supplied dome/probe tube assembly.
- ii. Using AlgoLabTest to adjust the gain, attempt to match the 65 dB Gain curve from the output of the device to the NAL-NL2 65 dB Gain Targets in Verifit.
- iii. Audioscan includes a method for saving measurements to a USB drive. Please use this method for saving the REAR measurements and targets for analysis of the output.
- iv. The file saved to the USB drive should include a .html or .csv file with frequency-specific values that can be used for plotting and analyzing the results.

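### The primary in-lab validity endpoint has two comparators (NAL-NL2 targets or measured PRO-FIT gain) and two formulas for PRO-FIT gain

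*Combined protocol and SAP*

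**What the plan says.** **Comparator.** The success criterion in section 3.2.1, repeated word for word in the synopsis, is that "SELF-FIT REAG is equivalent to PRO-FIT NAL-NL2 prescription REAG targets", on the four-frequency average. Attachment B item A.ii tells staff, for the SELF-FIT measurements, to "determine how close the 65 dB-Input referenced Response curve from the output of the device is to the NAL-NL2 65 dB REAR Targets". Items A.iii and B.iii have the targets saved with the REAR for later analysis.

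The sections on hypothesis, analysis and decision use the PRO-FIT fitting:
- Section 3.1.1: "Null hypothesis: Mean $|REAG_{PRO-FIT} - REAG_{SELF-FIT}| \geq 2.5$ dB".
- Section 8.1.2: a paired equivalence test of SELF-FIT A "to the means of the initial-fit settings of the PRO-FIT procedure".
- Section 8.4: "Effectiveness outcomes from the SELF-FIT process should be equivalent to those of the PRO-FIT method in the in-lab session".

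**Gain formula.** Section 6.2.3 obtains REAG, for targets and measurements alike, by subtracting the input level from REAR. Section 6.2.6 gives the same formula for each fit, PRO-FIT included, and refers to Attachment B for details. Attachment B item B defines PRO-FIT REAG as REAR minus REUR.

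**The concern.** A prescribed target and the gain measured after a professional fitting coincide only if the fitting hits its target. The plan does not assume that it will. In Attachment B item B.ii the audiologist is to "attempt to match the 65 dB Gain curve from the output of the device to the NAL-NL2 65 dB Gain Targets". Section 13.1 says "PRO-FIT REAG values will be checked to determine that they are reasonable, within 5-7 dB of NAL targets". Section 1.5.2.1 adds: "The maximum possible gain, however, has been limited to minimize the risk to hearing from device use". Both fits run on the same device, so both could miss target in the same direction. Such a miss disappears from SELF-FIT minus PRO-FIT but counts in full in SELF-FIT minus target.

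Section 8.4 makes overall success depend on every primary endpoint, so one data set could pass the study under one wording and fail it under the other. Section 13.1 also lets Visit 1 results go to the sponsor before the study ends. If the comparator is not settled by then, it could be chosen with the result in view.

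The formula conflict is narrower. It does harm only if PRO-FIT is computed one way and SELF-FIT the other.

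**Working it through.** **1. The plan's own figures.** The synopsis claims about 80% power at the 0.05 level for the in-lab comparison with 36 subjects. This cannot be reproduced, because no SD for REAG differences is given. The one power figure with full inputs (APHAB, section 5.1) does reproduce: SE = 0.115 × √(2/32) = 0.02875, noncentrality = 0.084/0.02875 = 2.92, 30 degrees of freedom, one-sided 2.5%, power 80.7% against the stated 80%. It does not bear on the in-lab endpoint.

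**2. What each comparator measures.** For one subject let T be the target, S = T + s the SELF-FIT gain and P = T + p the PRO-FIT gain.
- Against targets: D = S − T = s.
- Against measured PRO-FIT: D = S − P = s − p.

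If s and p both have mean m (a shared miss), the first D has mean m and the second has mean 0. The tolerance in section 13.1 is 5/2.5 = 2.0 to 7/2.5 = 2.8 times the margin.

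**3. Pass rules.** From the documents: n = 36, margin 2.5 dB, level 0.05 (taken as one-sided). Two readings of equivalence were run:
- *Mean-absolute* (3.1.1): the upper one-sided 95% t-limit of the mean of |D| is below 2.5.
- *Signed* (two one-sided t-tests): both one-sided 95% limits of mean D lie within ±2.5.

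For normal D with mean μ and SD σ, E|D| = σ√(2/π)·exp(−μ²/2σ²) + μ[1 − 2Φ(−μ/σ)]. Pass rates come from simulation with 200,000 trials per cell. All SDs, correlations and offsets below are assumptions.

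**4. Shared miss, SELF-FIT SD 2 dB, judged against targets.**

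| Offset (dB) | E of absolute D (dB) | Pass, mean-absolute | Pass, signed |
|---|---|---|---|
| 0 | 1.60 | 99.1% | 100% |
| 1 | 1.79 | 90.2% | 99.7% |
| 2 | 2.33 | 17.4% | 43.0% |
| 2.5 | 2.70 | 1.2% | 4.9% |
| 3 | 3.12 | 0.0% | 0.1% |

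The same subjects judged against measured PRO-FIT (PRO-FIT SD 1.5, correlation 0.5): SD of D = √(4 + 2.25 − 2 × 0.5 × 2 × 1.5) = 1.80 dB and mean 0. Both tests pass about 100% of the time, whatever the shared miss.

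Sensitivity to the SD against targets at a 2 dB offset: SD 1.5 gives 51% (mean-absolute) and 62% (signed); SD 3 gives 0.5% and 25%.

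**5. The opposite direction.** With no shared miss and independent deviations, SELF-FIT SD 2, the mean-absolute test against targets passes 99% of the time (E|D| = 1.60 dB). Against measured PRO-FIT the scatter of PRO-FIT is added:

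| PRO-FIT SD (dB) | E of absolute D (dB) | Pass, mean-absolute |
|---|---|---|
| 1 | 1.78 | 90% |
| 1.5 | 1.99 | 62% |
| 2 | 2.26 | 24% |
| 3 | 2.88 | 1% |

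At PRO-FIT SD 3 with correlation 0.5 the rate is 44%. Under the signed test, the worst case in the table still passes about 98% of the time.

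**6. Formula.** If SELF-FIT uses REAR minus input and PRO-FIT uses REAR minus REUR, then D = (REAR of SELF-FIT − REAR of PRO-FIT) + (REUR − input). The last term is the subject's open-ear gain, which the documents do not quantify. As an average offset it acts as in the step 4 table, if the SD of D is 2 dB. With one formula for both fits it cancels.

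**The case against.** The strongest reply is that the plan leans clearly one way. The reference to targets is a single sentence printed twice. Its own lead-in says REAG is measured under both fittings, and the hypothesis, test and decision text all use PRO-FIT, as do sections 1.5.3.1 and 6.2.3. No margin or test is written against targets. This stands as evidence of intent, and it is why the fix goes that way. It does not remove the conflict: the sentence headed as the success criterion says something else, and Attachment B directs both the comparison with targets and the saving of targets for analysis.

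A large PRO-FIT miss is also less likely than a selective reading suggests. Section 6.2.2 has the fit verified and fine-tuned to target by real-ear measurement, and Attachment B item E.iii has it adjusted until the curve is within the target range. The 5–7 dB figure is a plausibility check that may apply per frequency, and nothing says the gain limit falls below target for eligible subjects. These points hold. A 2 dB shared miss is an illustration, and the PRO-FIT SD 3 case deserves little weight. With no shared miss and the SDs of step 4, both comparators pass about 99% of the time or more. Under the signed test, shared misses of 0.5, 1 and 1.5 dB still pass 100%, 99.7% and 90% of the time. The step 5 contrast arises almost entirely from the mean-absolute test.

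On the formula, section 6.2.3 is explicit and REAR minus REUR appears only once. The SELF-FIT formula printed beside it is garbled in the text available; it evidently means REAR minus input and is not counted as a third definition. Mixing formulas would mean departing from section 6.2.3. That part is therefore a consistency correction.

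**Conclusion.** The concern holds, and the plan should be corrected. The stated success criterion for one of the three primary effectiveness endpoints names a different comparator from the hypothesis, test and pass/fail text, and no provision says which governs. That finding rests on the text alone.

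The consequence depends on unknowns. With an SD near 2 dB, the comparators reach similar verdicts while any shared miss stays at or below about 1 dB, and diverge sharply near 2 dB (17% or 43% against about 100%). The documents give no REAG SD, deviation from target or open-ear gain, so no single figure can be put on the risk. The formula conflict is real but secondary: it matters only if the two fits are computed differently. The SELF-FIT A versus B reliability endpoint is not affected.

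**What to change.** - In section 3.2.1 and the synopsis, restate the criterion as: *four-frequency average initial-fit SELF-FIT A REAG is equivalent to measured initial-fit PRO-FIT REAG*. This agrees with 3.1.1 and 8.1.2.
- In Attachment B item B, define REAG as REAR minus input, as in 6.2.3 and 6.2.6, and state that REUR does not enter the endpoint.
- Report each fit's deviation from NAL-NL2 targets as a supportive analysis, and label the Attachment B item A.ii comparison as part of it. A miss shared by both fits then stays visible.
- Make these changes before any Visit 1 results are analysed or shared.

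The cost is wording in the synopsis, section 3.2.1 and Attachment B. No new measurement is needed, because REAR and targets are already saved for both fits.

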3.2.2 Primary Safety Endpoint

Tabulations of Adverse Events (AEs) and Serious Adverse Events (SAEs).

- Success criterion is no recorded device-related AEs or SAEs.

3.2.3 Secondary Effectiveness Endpoints

For the validation component of the immediate in-lab session comparison, aided QuickSIN performance will be compared between SELF-FIT and PRO-FIT.

- Success criterion is the SELF-FIT QuickSIN speech-recognition threshold in noise (signal-to-noise ratio, SNR) is equivalent to that of PRO-FIT.

For the reliability component of the immediate in-lab session comparison, QuickSIN performance will be measured twice (A, B) using the SELF-FIT method to assess test-retest reliability.

- Success criterion is QuickSIN thresholds are equivalent for SELF-FIT A and B.

For the wear-time crossover field trial, QuickSIN performance will be compared between SELF-FIT and PRO-FIT.

- Success criterion is defined as SELF-FIT QuickSIN SNR is equivalent to PRO-FIT QuickSIN SNR following completion of the wear-time field trial.

4.0 DESIGN OF RESEARCH STUDY

4.1 Type of Research Study

This study has two components to assess the safety and effectiveness of the Jabra Enhance Plus device in adults with mild to moderate sensorineural hearing loss. The reliability and validity of the self-fitting method are examined in an in-lab session with counter-balanced conditions. A second component, a single-blind counter-balanced cross-over wear-time field trial, further evaluates the validity of the self-fitting method. Three sites are involved in data collection.

4.2 Controls and Minimization of Bias

The Sponsor, GN Hearing A/S, should avoid improper influence on any parties participating in, or contributing to, the clinical study or the induction thereof. The selection and treatment of subjects and evaluation of study data are potential sources of bias. Methods that are incorporated within the study design to minimize potential bias include, but are not limited to, screening subjects to confirm study eligibility with defined inclusion/exclusion criteria prior to enrollment; maintaining a log of all subjects screened and enrolled for the study, collecting demographics and medical history at baseline to later assess possible characteristics that may influence endpoints; standardizing data collection requirements and study procedures; requiring all study investigators to meet the requirements of 21CFR Part 54 and a Financial Disclosure by Clinical Investigators; using standardized training materials for all study personnel; and conducting regular electronic monitoring to verify adherence to the protocol and source data.

5.0 STUDY SUBJECTS

5.1 Sample Size Determination

The sample size was powered by the primary outcome measure of the wear-time field trial, the APHAB, as it is the most variable of the outcome measures across all components of this study. When the sample size in each sequence group in the crossover trial is 16 (giving a total sample size of 32), a crossover design will have 80% power to reject the null hypothesis that the SELF-FIT APHAB mean is inferior to the PRO-FIT APHAB mean based on the mean difference, in favor of the alternative hypothesis that the SELF-FIT mean is non-inferior to the PRO-FIT mean, assuming that the expected difference in means is 0, the non-inferiority difference margin is .084 (or 8.4%), the Crossover ANOVA \sqrt{MSE} is 0.115 (or 11.5%) (giving a standard deviation of differences, σ , of 0.163 or 16.3%) and that the test is made at the 2.5% significance level.

The overall design for the in-lab session is a repeated-measures design comparing outcomes for three procedures: SELF-FIT A, SELF-FIT B, PRO-FIT. Given that SELF-FIT A and B are the same procedure repeated two times, this results in three possible procedure sequences: (1) SELF-FIT A, SELF-FIT B, PRO-FIT; (2) SELF-FIT A, PRO-FIT, SELF-FIT B; and (3) PRO-FIT, SELF-FIT A, SELF-FIT B. An equal number of subjects will receive each sequence at each site to ensure full counterbalancing of order. A total of 36 subjects, 18 per site, will be included which meets the minimum of 32 required for sufficient statistical power, achieves the desired counterbalancing, and allows for some subject attrition or missing data.

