Primary Safety Objectives/Endpoints:	
Tabulations of Adverse Events (AEs) and Serious Adverse Events (SAEs).
 
○ Success criterion is no recorded device-related AEs or SAEs.
Inclusion Criteria:	
An initial telephone or internet screening of interested persons will take place.
 
• During this remote screening, prospective subjects will provide their age (subject to verification at Visit 1) and answer a Yes/No question as to whether they have trouble hearing in noise. Those answering "No" will not be considered further for enrollment.• Those answering "Yes" will then be asked to describe their perceived hearing loss on a 4-point scale (no trouble, a little trouble, a lot of trouble, and cannot hear). Prospects answering at the two extremes will not be considered further for this study.• Those answering "a little trouble" or "a lot of trouble" will be invited to the in-person Screen that immediately precedes hearing aid fittings in Visit 1. To be eligible to participate in this study, an individual must meet all of the following criteria:

	
 • Mild-to-moderate bilateral sensorineural hearing loss (thresholds from 250 – 8000 Hz with at least one threshold greater than 20 dB HL and thresholds at 500, 1000, 2000 and 4000 Hz less than or equal to 55, 65, 70, and 80 dB HL, respectively) • Mix of male and female subjects (aiming for a representative balance) • Mix of prior hearing-aid use (aiming for 70-80% persons with no prior hearing aid use) • 18-75 years old (aiming for primarily 50-70 years old, with avg. age ~65 years) • Able to read and comprehend English • Patient willing to provide informed consent
Exclusion Criteria:	
An individual who meets any of the following criteria will be excluded from participation in this study:
 
 • Hearing outside of limits noted above • Self-reported ear-related pathology (including chronic severe dizziness or chronic severe tinnitus)
Sampling Frame:	
The proposed sample size of n=36 subjects will be sufficient to rule out a null hypothesis of non-equivalence of SELF-FITs A and B (reliability) or SELF-FIT A and PRO-FIT (validity) with about 80% power with 0.05 significance level. In addition, distributions of deviations from the standard-of-care measures will be generated for the primary and secondary measure and for the reliability and validity components of the study.

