- v. The SELF-FIT process continues uninterrupted with user-preferred adjustments of "filters" or frequency-gain responses. These user-driven fine-tuning adjustments are made while streaming a sound file to the devices and comparing filter settings. (See Attachment 4A for details.) When the subject selects the final settings, these

device settings are saved and become the new default settings for when the device is powered on. These settings are referred to as the "final fit" for the SELF-FIT procedure. Measurements made for SELF-FIT A and PRO-FIT at the end of each wear-time crossover field trial will make use of these *final-fit* settings.

- vi. Once the subject has completed the test, the app will indicate that the subject is finished with personalization of the devices and will return to the home screen of the app.

6.2.4 SELF-FIT B: To assess test-retest reliability, subjects will complete the self-fitting procedure a second time (repeat steps for SELF-FIT A above).

6.2.5 Overview of Procedures at Visits 1, 2, and 3

Successive subjects will be assigned to one of these six condition sequences illustrated in Figure 1 with a total of two cycles through the full set of six sequences at each of the three sites. In the end, two subjects will have been tested in each of the six sequences at each site, six per sequence for the entire study, and any effects of order will be equalized across conditions following the counterbalancing illustrated in Figure 1.

The table below summarizes the primary and secondary outcome assessments to be completed during each study visit. For Visits 2 and 3, REAG will also be established but only for potential explanatory purposes and not as an outcome measure.

Visit	Primary Outcome	Secondary Outcome
1	REAG from REAR; initial fit	QuickSIN; initial fit
2	APHAB; final fit	QuickSIN; final fit
3	APHAB; final fit	QuickSIN; final fit

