After the final in-lab measures have been completed during Visit 1, 9 subjects at each site will wear the devices with the final-fit SELF-FIT A settings and the other 9 at each site will begin the crossover trial with the final-fit PRO-FIT settings. After the initial 10-to-14-day wear-time trial, the subjects will return to the lab for the measurement of REAG, aided APHAB, and aided QuickSIN during Visit 2. Each subject will then embark on a second 10-to-14-day wear-time period using the devices with the other fitting settings (SELF-FIT A settings if PRO-FIT settings were worn first, and vice versa). Subjects will return after the second 10-to-14-day wear-time period for completion of REAG, aided APHAB and aided QuickSIN measures with this second fitting, during Visit 3.

Subjects will follow the instructions for the "Self-fitting flow" (Section 16.0, Attachment A) to complete SELF-FIT A and SELF-FIT B procedures. After the installation of software on the smartphone, the pairing of the devices to the smartphone, and the physical fit of the devices, no further assistance will be provided to the subject by the professional or research staff until the completion of Visit 1. When Visit 1 has been completed, the subject will be provided with the devices, the charger, the USB-C cable, and a copy of the User's Manual (Attachment A). The research audiologist will answer questions raised by the subject as he or she pages through the manual. Prior to leaving for the first phase of the field trial, the subject will demonstrate to the audiologist that he or she can insert and remove the devices, adjust the

volume with the app, and place the devices in the charger. The audiologist will log any errors made in this verification of basic use and will correct the subject on those errors once, if needed, prior to the subject leaving with the devices.

For the wear-time field trial, subjects will be asked to wear the devices in a variety of listening situations during the trial including while listening to music and while using the telephone. Subjects will be asked to wear their devices a minimum of two hours per day.

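### Sections 5.1 and 6.2.5 give per-site numbers (18, and 9 + 9 by wear order) that imply 54 subjects at three sites, against a stated total of 36 and 12 per site elsewhere in 6.2.5

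*Combined protocol and SAP*

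**What the plan says.** **Number of sites.** Section 4.1: "Three sites are involved in data collection". The synopsis also gives 3, section 6.3 lists three by name, and section 13.0 names the same three as performing the study.

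**Total.** The synopsis gives N = 36, and its sampling-frame entry repeats it: "The proposed sample size of n=36 subjects will be sufficient". Section 5.1 also gives 36. The power requirement behind it is in 5.1: "When the sample size in each sequence group in the crossover trial is 16 (giving a total sample size of 32".

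**Per-site numbers.** Three statements bear on this:

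- Section 5.1: "A total of 36 subjects, 18 per site, will be included which meets the minimum of 32 required for sufficient statistical power".
- Section 6.2.5, on sequence assignment: "with a total of two cycles through the full set of six sequences at each of the three sites", so that "two subjects will have been tested in each of the six sequences at each site, six per sequence for the entire study".
- Section 6.2.5, on the start of the wear-time trial: "9 subjects at each site will wear the devices with the final-fit SELF-FIT A settings and the other 9 at each site" start with PRO-FIT.

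**Balance.** Section 5.1, on the in-lab procedure orders: "An equal number of subjects will receive each sequence at each site to ensure full counterbalancing of order".

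**Data management.** Section 13.1 item 5 ties the final data reduction and report to the completion of data collection at both sites, although 13.0 names three.

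**The concern.** The per-site enrolment target and the per-site split by wear order are figures that sites act on, and the plan gives two incompatible versions of each. A site working from the sequence scheme in 6.2.5 stops at 12 subjects, two per sequence. A site working from 5.1 and the wear-order sentence in 6.2.5 aims for 18, nine starting with each fitting. Nine and nine cannot be reached with 12 subjects.

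If sites follow different sentences, the study could over-enrol. Alternatively, it could reach 36 with sites stopping part-way through a cycle, or with unequal wear orders. Counterbalancing is the plan's stated control for order effects in both the in-lab session and the crossover, so the per-site counts are part of the design.

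The both-sites wording in 13.1 item 5 raises a smaller point: read literally, it does not say whether the final analysis waits for the third site.

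**Working it through.** **Inputs.** Three sites (synopsis, 4.1, 6.2.5, 6.3, 13.0). Total 36 (synopsis, 5.1). Six sequences with two cycles per site (6.2.5). 18 per site (5.1). 9 + 9 per site by wear order (6.2.5). For power: margin 0.084, expected difference 0, crossover root MSE 0.115, test level 2.5%, 16 per sequence group (all 5.1).

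**Step 1: reproduce the plan's own sample size.** For a 2 × 2 crossover with n1 and n2 subjects in the two wear orders and N = n1 + n2, the standard error is 0.115 × √[(1/n1 + 1/n2)/2]. The noncentrality is 0.084/SE, and power is P(T > t(0.975, N − 2)) for a noncentral t with N − 2 degrees of freedom.

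- 16/16: SE = 0.02875, noncentrality 0.084/0.02875 = 2.922, critical value 2.042, power **80.7%** (stated: 80%).
- 18/18: SE = 0.02711, noncentrality 3.099, critical value 2.032, power **85.3%**.

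With the plan's rounded standard deviation of differences, 0.163, the results are 80.5% and 85.2%. The minimum of 32 reproduces. A total of 36 leaves a reserve of 36 − 32 = 4 subjects (4/36 = 11.1%).

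**Step 2: multiply out the per-site statements.**

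| Quantity | Sequence scheme in 6.2.5 | 18 per site (5.1) and 9 + 9 (6.2.5) |
|---|---|---|
| Per site | 2 × 6 = 12 | 18 = 9 + 9 |
| Total at three sites | 12 × 3 = 36 | 18 × 3 = 54 |
| Cycles of six per site | 2 | 18/6 = 3 |
| Per sequence, whole study | 2 × 3 = 6 | 3 × 3 = 9 |
| Per in-lab order per site | 12/3 = 4 | 18/3 = 6 |
| Per wear order per site | 12/2 = 6* | 9 |
| Per wear order, whole study | 6 × 3 = 18* | 9 × 3 = 27 |

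*Assumes that three of the six sequences start with each fitting; Figure 1, which would show this, is not reproduced in the text available.

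**Step 3: compare with the fixed points.** Only the first column agrees with the total of 36, with three sites, and with the six per sequence that 6.2.5 states. The second column agrees with none of the stated totals. The figures 18 and 9 + 9 fit a total of 36 only with two sites (18 × 2 = 36). The revision table records a change from two to three sites, which is the likely origin, but the contradiction lies in the current text and does not depend on that table.

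**The case against.** The arithmetic is not in dispute; the case on the other side concerns consequence.

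- **Containment.** The total of 36 is stated three times, once in the same sentence as 18 per site. Section 6.2.5 fixes six per sequence overall. Section 13.1 item 2 requires weekly counts of complete data by site and combined, and section 4.2 requires a log of subjects screened and enrolled. This stands, and it makes over-enrolment unlikely.
- **Balance at 18.** Eighteen divides by three and by six, so a site that completed 18 would still be balanced. This also stands. Balance is lost only if a site stops within a cycle, or fills toward nine in one wear order and then stops at 12.
- **The working rule.** The assignment rule is the cycling through six sequences, and the 9 + 9 sentence can be read as describing its result. On that reading a site following the rule would arrive at 6 and 6 anyway, given the assumption about Figure 1. This is plausible, but it leaves a wrong number in the protocol.
- **Power under imbalance.** The power in step 1 is for equal wear orders. If every site ended at 9 and 3 (27/9 overall), SE = 0.03130, noncentrality 2.684 and power about 74%. This is an extreme case that the sequence scheme makes unlikely. It qualifies any statement that power cannot be touched, but it does not alter the planned calculation.

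**Conclusion.** The concern holds. With three sites and 36 subjects, 18 per site (5.1) and 9 + 9 per site (6.2.5) are wrong as written, and section 6.2.5 contradicts itself. The excess is 6 subjects per site, 3 per wear order per site and 18 overall. That 12 per site is the intended figure follows from the total, the number of sites and the sequence scheme, all of which agree. The 6 and 6 split is an inference that rests on half of the six sequences starting with each fitting.

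The total, the minimum of 32, the stated power and the analysis are unaffected. The harm is a possible one, to enrolment and within-site counterbalancing, and existing safeguards limit it. It should be fixed because these are operating numbers for sites, but it does not threaten the study's conclusions if the sequence scheme is followed.

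The reference to both sites in 13.1 item 5 does not match a three-site study. The references in 13.1 items 4 and 5 to two site investigators and to both site PIs are not shown to be wrong, since item 2 shows two removed names for the site investigators; they only need confirming.

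**What to change.** - **Section 5.1:** change 18 per site to 12 per site, keeping the total of 36.
- **Section 6.2.5, wear-time paragraph:** change 9 and 9 per site to 6 and 6 per site (18 per wear order overall), after checking the split against Figure 1.
- **Section 13.1 item 5:** make the final data reduction and report follow completion at all three sites.
- **Section 13.1 items 4 and 5:** confirm whether two site investigators and two site PIs is still correct for three sites.

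The cost is a wording amendment to two enrolment sentences and one data-management sentence. It needs no extra subjects and no change to the analysis. If 18 per site at three sites was in fact intended, the total of 36 and the six per sequence would have to change instead, to 54 and 9; nothing else in the plan supports that reading.
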